### Methods

Proposed study uses an open-label prospective randomized single-center study approach. 360 patients, with or without ID, hospitalized with MI are recruited at the Kazan city clinical hospital №7, which is the clinical base of Kazan State medical university. Patients with ID (n=240) are randomised (1:1) to either intravenous (i.v.) FCM or oral ferrous sulphate. Patients with normal iron status (n=120) are in the control group.

The trial, which is conducted in strict compliance with Good Clinical Practice (GCP) and with the Declaration of Helsinki, was approved by the Local Ethics Committee.

**Study population.** Male and female patients aged  $\geq 18$  years, hospitalised with MI and diagnosed according to **Fourth Universal Definition of MI and Myocardial Injury (ESC 2018)**, with hypokinesia or akinesia in at least two connected LV segments according to echocardiography results obtained within the first 24 hours after myocardial infarction occurs, will be considered for participation. All patients who agreed to participate will be asked to provide written informed consent before any trial-related procedure is performed.

**Inclusion and exclusion criteria.** Inclusion/exclusion criteria are shown in Table 1

**Definition of MI.** MI is diagnosed according to **Fourth Universal Definition of MI and Myocardial Injury (ESC 2018)** when there is a rise and/or fall of cardiac troponin values (cTn) values with at least one value above the 99th percentile upper reference limit (URL) and at least one of the following signs: symptoms of myocardial ischaemia, new ischaemic ECG changes, development of pathological Q waves, imaging evidence of new loss of viable myocardium or new regional wall motion abnormality in a pattern consistent with an ischaemic aetiology [15].

**Definition of ID.** ID is defined as serum ferritin  $<100$  ng/mL (absolute ID) or  $100$  ng/mL  $\leq$  serum ferritin  $\leq 299$  ng/mL if transferrin saturation (TSAT)  $<20\%$  (functional ID) [9].

**Assessment of LV systolic function.** LV systolic function is assessed by transthoracic echocardiography with evaluation of Wall motion score index (WMSI) using 16-segment model [16].

**Assessment of quality of life.** Quality of life is assessed using the Kansas City Cardiomyopathy Questionnaire (KCCQ) [17]

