**Screening.** During screening all risks and benefits of participation are described to each patient who fit the chosen inclusion criteria. Each patient considered in the study will be provided 2 copies of written consent and will receive one copy of the consent, in addition each patient will receive a form containing information about study participation. Anamnesis, physical examination, echocardiography, KCCQ, complete blood count (CBC), serum iron level, total iron binding capacity (TIBC), serum ferritin level, TSAT, alanine transaminase, aspartate transaminase, creatinine are performed at the screening visit within 24 hours after MI. The data of each study participant will be entered into individual patient registration cards specially designed for each visit.

**Randomisation and study treatment dosing regimen.** Patients with ID are randomised to either i.v. FCM or oral ferrous sulphate randomly with block randomizations. The FCM doses were determined using the patient's screening visit body weight measurement and haemoglobin value (table 2). Patients receives all doses during hospitalization accordance with the drug local

labels. 100 mg of ferrous sulphate is administrated 2 times per day during hospitalization and continue within next 2 month.

**Study outcomes.** The primary significant outcome is the decrease in WMSI value. The secondary outcome the composite of cardio-vascular (CV) mortality, non-fatal stroke, non-fatal MI, recurrent HF hospitalizations.

**Patient Assessments.** All participants are observed for 12 months from the first visit after the admission to the study. Participants are evaluated in-person at 3-, 6-, and 12-month intervals with correction of treatment if necessary. Participants are also evaluated monthly through telephone consultation. Echocardiography with WMSI evaluation, KCCQ, CBC, serum iron level, TIBC, serum ferritin level, TSAT is performed during every physical evaluation visit. Primary and secondary outcomes are established during follow up period.

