**Statistical analysis.** Statistical data is analysed using standard methods of descriptive statistics. For categorical variables, summary tabulations of the number and percentage of subjects within each category of the corresponding parameter will be presented. For continuous variables, the mean, median, standard deviation, first and third quartiles, and minimum and maximum values will be presented. Clinical-laboratory associations will be assessed as well as associations with outcomes (Kaplan-Meier subgroup survival curves). The level of significance to be used for tests will be 0.05.

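### Associations with outcomes are planned only as Kaplan-Meier curves by undefined subgroups, with no model that keeps a continuous laboratory marker continuous

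*Combined protocol and SAP*

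**What the plan says.** After a list of descriptive summaries, the Statistical analysis paragraph of Methods promises an assessment of links between clinical and laboratory findings, and of "associations with outcomes (Kaplan-Meier subgroup survival curves". It then sets the test level: "The level of significance to be used for tests will be 0.05". Whether tests are one-sided or two-sided is not stated. No Cox, logistic or other regression model appears anywhere in the document. The paragraph does not say which variables form the subgroups, how many groups there are, or where any cut would fall.

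The Screening paragraph lists the laboratory tests: "complete blood count (CBC), serum iron level, total iron binding capacity (TIBC), serum ferritin level, TSAT, alanine transaminase, aspartate transaminase, creatinine are performed". All of these give continuous values. The only marker limits in the document are in Definition of ID: ferritin below 100 ng/mL (absolute), or 100 to 299 ng/mL with TSAT below 20% (functional).

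On numbers, "Patients with ID (n=240) are randomised (1:1) to either intravenous (i.v.) FCM or oral ferrous sulphate", and "Patients with normal iron status (n=120) are in the control group". The outcome to which survival curves naturally apply is the secondary composite, over 12 months of observation. No expected event rate is given.

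**The concern.** A Kaplan-Meier curve needs groups. Under the only method named, a continuous marker such as ferritin or creatinine can be related to outcome only after it has been cut. Three things are then at stake.

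- **Information.** Patients on the same side of a cut are treated as alike, which lowers power at a given number of events.
- **Interpretation.** The curves give no hazard ratio per unit or per SD, and no adjustment for study group or other baseline factors.
- **Error rate.** With no cut-points on record, nothing stops a cut being chosen because it separates the curves well. The nominal 0.05 would not then hold.

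**Working it through.** The plan states no power, event rate or effect size, so there is no figure of its own to reproduce.

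**Inputs from the document:** 360 patients, of whom 240 are randomised and 120 have normal iron status; 12 months of observation; level 0.05.

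**Assumptions:** two-sided tests; a log-linear effect of the marker on the hazard; 10%, 15% or 20% of 360 patients with an event (36, 54 or 72); a hazard ratio (HR) of 1.4 per SD.

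**Step 1: information kept after grouping.** For a small effect, the efficiency of the grouped marker relative to the continuous one is the squared correlation between them. For a normal marker with a share p on one side of the cut:

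efficiency = φ(z_p)² / [p(1 − p)]

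At the median, φ(0)² = 1/(2π), so efficiency = [1/(2π)] / 0.25 = 2/π = 0.637. With k equal groups and a trend test, it is the squared correlation of the marker with the group score.

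| Grouping | Efficiency | Loss |
|---|---|---|
| Median split | 0.637 | 36% |
| One-third / two-thirds | 0.595 | 40% |
| 25% / 75% | 0.539 | 46% |
| 10% / 90% | 0.342 | 66% |
| Tertiles, trend | 0.793 | 21% |
| Quartiles, trend | 0.856 | 14% |
| Quintiles, trend | 0.888 | 11% |
| Uniform marker, median split | 0.750 | 25% |
| Lognormal marker, log-SD 0.5 to 1.0, effect linear on raw scale, median split | 0.515 to 0.271 | 49% to 73% |

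A median split therefore needs 1/0.637 = 1.57 times the events. If there were 36 events, they would work like 36 × 0.637 = 22.9.

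**Step 2: effect on power.** Power = Φ(√(D × efficiency) × ln HR − 1.96), where D is the number of events. For D = 36 and continuous: 6 × 0.3365 − 1.96 = 0.059, giving 52%. With a median split: √22.9 × 0.3365 − 1.96 = −0.35, giving 36%.

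| Assumed events | Continuous | Median split |
|---|---|---|
| 36 | 52% | 36% |
| 54 | 70% | 50% |
| 72 | 82% | 63% |

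**Step 3: check by simulation.** Cox score tests were run on 8,000 simulated trials of 360 patients followed for 12 months, with about 55 events. At HR 1.4 per SD, power was 69.5% continuous and 49.5% split. The efficiency of the median split was 0.62 to 0.63. A cut setting apart the highest third gave 0.66, against 0.595 from the formula, so the off-centre entries in Step 1 are approximate.

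**Step 4: false positives if the cut is chosen from the data.** Null simulations with n = 240, two-sided 0.05:

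| Choice of cut | Continuous outcome | Repeat, 20,000 runs | 36 of 240 with an event (binary), 20,000 runs |
|---|---|---|---|
| Fixed median | – | 5.1% | – |
| Best of three quartile cuts | 12.1% (6,000 runs) | 12.4% | 13.5% |
| Best cut, 25th to 75th percentile | 29.1% (4,000 runs) | 28.3% | 28.4% |
| Best cut, 10th to 90th percentile | 43.4% (4,000 runs) | 43.7% | 43.2% |

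With 24 events, the quartile figure was 17%. These rates do not depend on the shape of the marker, because only ranks matter. The simulations used no censored survival times, so they show the size of the effect and not an exact rate for a log-rank test.

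**The case against.** The strongest objection is that the sentence does not say what the concern needs it to say. A reader might infer that the plan commits the trial to cutting every laboratory marker and so to losing about a third of the information. The text does not support that. The subgroups could be the three study groups or clinical categories, and naming curves for display does not exclude a regression model. The one-third figure belongs to one grouping of one kind of marker. Quartiles with a trend test lose 14%.

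A reader might also infer that the ferritin and TSAT limits are used up at entry, so that cuts within the iron-deficient arms must come from the data. That is wrong. Ferritin 100 ng/mL still separates absolute from functional deficiency, and TSAT 20% still divides patients with absolute deficiency, who qualify whatever their TSAT. Nor does the plan propose a search for the best cut, so Step 4 describes conduct that is left open, not conduct that is planned. The event counts are assumptions, and these associations are exploratory.

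All of this stands and limits the point. It does not remove it. On any reading the subgroups are undefined and no model is named. For serum iron, TIBC, the blood count, transaminases and creatinine, the document offers no cut-point at all.

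**Conclusion.** The concern holds in a conditional form. The plan gives one method for associations with outcomes, and that method can use a continuous marker only once it has been grouped. It would then yield no effect per unit and no adjustment. The loss is about 36% for a median split of a roughly normal marker with a log-linear effect. Across the groupings and distributions tried, it runs from about 11% to 73%. The document does not say which of these would apply. The inflation to about 12% or 43% arises only if cuts are chosen after seeing the data. The power figures also rest on the assumed event counts and HR.

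The consequence is small. The primary comparison of wall motion score index and the randomised comparison on the composite do not depend on this analysis. It is still worth correcting, because a better method is available on data already being collected.

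**What to change.** In the Statistical analysis paragraph:

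1. Estimate associations with time to first composite event by a Cox model. Enter each screening marker as a continuous term (log scale for ferritin), with study group in the model. Report the hazard ratio per SD with its 95% CI.
2. Label these analyses exploratory. Several markers would each be tested at 0.05, and continuous modelling does not cure that multiplicity. Add a spline for curvature only if the number of events allows.
3. Note that ferritin and TSAT define iron deficiency. With study group in the model, their coefficients therefore describe associations within groups.
4. Keep Kaplan-Meier curves as illustration, by study group or at cut-points fixed before the data are seen. The ferritin 100 ng/mL and TSAT 20% limits in Definition of ID would serve. Name the subgroup variables.

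The cost is a few sentences and routine modelling, with no new data. The one downside is a proportional-hazards assumption, which should be checked and reported.
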